Appendix 12Schirmer Test (without anesthesia)

Please refer to Tear Film PK Sample collection in the Lab Manual for measurement technique.

Appendix 13 OTX-CSI or HV Insert Placement

The following is the suggested placement technique and it can be modified based on investigator's medical judgment.

- 1. Apply lateral pressure to elongate the canalicular system. Pull the skin near the punctum down and temporally. A technician may assist if needed.
- 2. Dilate using the punctal dilator in towards the nose, ensuring the system is elongated. Dilate through the punctum deeper into the canaliculus, dilate for depth, as well as width. If desired, rotating the dilator in a spinning motion may help with the dilating process.
- 3. Dry the surface around the punctal opening using an ophthalmic sponge. More than one sponge may be necessary to ensure adequate drying of area. A technician may assist if needed.
- 4. Grasp the OTX-CSI or HV insert with forceps and insert at a slight angle towards the nose. Aim for 70% of insertion within the first motion. Use forceps to tap or push insert the remainder of the way in. The insert should sit slightly beneath the punctal opening.

Note: Excessive squeezing of an OTX-CSI or HV may cause deformation. The product should be handled with care, so it maintains its original shape prior to insertion. If the insert hydrates before placement slightly below the punctal opening (resembling a trumpet shape), it should be discarded and a new insert should be used. If the insert hydrates before ideal positioning or if a portion of the insert is protruding and unable to be inserted, it should be removed, discarded and a new insert should be used.

5. An OTX-CSI or HV insert can be visualized when illuminated by a blue light source (e.g., slit lamp or hand-held blue light) with yellow filter.

The investigator will grade the level of ease of insertion of the ophthalmic insert as "easy" (1), "moderate" (2) or "difficult" (3).
Appendix 14 OTX-CSI or HV Insert Ease of Visualization

The Investigator will assess the presence of an OTX-CSI or HV insert at each study visit, using a blue light and yellow filter. The Investigator will be asked to grade the level of ease of visualization of the punctum plug as "easy", "moderate", or "difficult".

Appendix 15 OTX-CSI or HV Insert Removal Instructions

An OTX-CSI or HV Insert can be removed either via application of manual pressure or saline irrigation, as described below.

Application of Manual Pressure

- 1. Identify the OTX-CSI or HV insert through the punctal tissue.
- 2. Place the blunt end of an instrument (e.g., punctum dilator or equivalent) next to the distal end of the test article.
- 3. Apply gentle pressure by pressing on the instrument in an outward motion towards the punctum until the test article is expressed out of the punctum.

Saline Irrigation

- 1. Ensure the punctum and canaliculus is sufficiently dilated.
- 2. Fill a sterile syringe and fixed cannula with sterile saline.
- 3. Insert the cannula into the vertical canaliculus.
- 4. Insert until it stops and simultaneously rotate the syringe horizontally.
- 5. Press slowly on the syringe plunger to flush the test article.
- 6. In order to help assess whether the flush is complete, it may be helpful to ask the subject to report when they taste saline or feel it in their nose.

The investigator will grade the level of ease of removal of the insert as "easy" (1), "moderate" (2) or "difficult" (3).

Appendix 16 Daily Subject Diary (For Artificial Tear Use)

If subjects are using artificial tears, they will be asked to complete a dosing diary for each administration. The dosing diary will collect the following information with respect to artificial tear administration:

Date	Time	Time	Time	Time	Time	Initials
DD/MMM/YYYY	HR/MIN	HR/MIN	HR/MIN	HR/MIN	HR/MIN	
//	AM/PM	AM/PM	AM/PM	AM/PM	AM/PM	

Due du et Merree	Commons	Indication	Decier	Marketed since
Product Name	Company	Indication	Kegion	Marketed since
Cequa [™] (0.9 mg/ml)	Sun Ophthalmics	DED (KCS with presumed suppression of tear production)	US	2018
Restasis [®] (0.5 mg/ml)	Allergan	DED (KCS with presumed suppression of tear production)	US, Canada, and 33 other countries	2003
Ikervis [®] (1.0 mg/ml)	Santen Pharmaceutical	DED (Severe keratitis which has not improved with tear substitutes)	Europe	2015
Papilock Mini [®] (1.0 mg/ml)	Santen Pharmaceutical	VKC	Japan	2005
Modusik-A Ofteno [®] (1.0 mg/ml)	Laboratorios Sophia	KCS with a functional decrease of lacrimal glands	Mexico, Chile Columbia, Peru, Ecuador, Argentina	2003
TJ Cyporin [®] (0.5 mg/ml)	Taejoon Pharma Co, Ltd	Ocular inflammation associated with KCS	South Korea	2003
Lacrinmune [®] (0.5 mg/ml)	Bausch & Lomb, Inc.	KCS with a functional decrease of lacrimal glands	Argentina	NA
Cyporin [®] (0.5 mg/ml)	Aristopharma, Ltd	Ocular inflammation associated with KCS	Bangladesh, Myanmar	NA
Cyclorin [®] (0.5 mg/ml)	Ibn Sina Pharmaceutical Industry, Ltd.	Ocular inflammation associated with KCS	Bangladesh	NA

Appendix 17	Marketed	Cyclosporine
-------------	----------	--------------

Adapted from Lallemand et al., 2017

IOP	ntraocular Press	ure			
IP	Investigational Product				
IRB	Institutional Review Board				
IRT	nteractive Respo	onse Technology			
ITT	ntent-to-Treat				
IUD	ntra-Uterine Dev	vice			
ксѕ	(eratoconjunctiv	ritis Sicca			

Statistical Analysis Plan

Sponsor:	Ocular	Therape	utix, Inc.			
Protocol:		otocol-0				
Document Version No	o.: V1.0		Document Date:		01-OCT-2021	
LogMAR	Logarithm of the Minimum Angle of Resolution					
mg	Milligram					
ml	Milliliter					
mm	Millimeter					
mmHg	Millimeters	of Merc	cury			
NDA	New Drug A	pplication	on			
NEI	National Ey	e Institu	te			
NOAEL	No Observed Adverse Event Level					
NSAID	Nonsteroidal Anti-Inflammatory Drug					
NSR	Non-Significant Risk					
РР	Per Protocol					
PRN	As Needed					
OD	Right Eye					
OS	Left eye					
OSDI	Ocular Surf	ace Dise	ase Index			
отх	Ocular Ther	apeutix				
OTX-CSI	Cyclosporine Ophthalmic Insert					
РК	Pharmacokinetics					
SAE	Serious Adverse Event/Experience					
SPEED	Standard Pa	atient Ev	aluation of Eye Dry	vness		
SRG	Safety Revie	ew Grou	р			

Statistical Analysis Plan

Sponsor: Ocular Therapeutix, Inc.					
Protocol: CLN-Protocol-0054					
Document Vers	sion No.:	V1.0	Document Date:	01-OCT-2021	
SUSAR	Sus	pected Une	pected Serious Adverse F	Reactions	
TBUT	Теа	r Film Break	Up Time		
tCFS	Tota	al Corneal Fl	uorescein Staining		
μg	Mic	Microgram			
UPT	Urir	Urine Pregnancy Test			
US	Unit	United States			
VA	Visu	Visual Acuity			
VAS	Visu	Visual Analog Scale			
VKC	Veri	Vernal Keratoconjunctivitis			
WOCBP	Woi	men of Chilo	d-Bearing Potential		

Sponsor:	Ocular Therapeutix, Inc.			
Protocol:	CLN-Protocol-0054			
Document Version No.:	V1.0 Document Date: 01-OCT-2021			

1. INTRODUCTION AND OBJECTIVES OF ANALYSIS

1.1. Introduction

Dry Eye Disease (DED)

Dry eye disease (DED), also known as Keratoconjunctivitis Sicca (KCS), is one of the most common ophthalmic disorders presenting to the clinician (American Academy of Ophthalmology, 2018). Prevalence of dry eye is higher among women than men (Farrand et al, 2017). Prevalence also increases with age with 2.7% of Americans age 18 to 34 years and 18.6% of Americans ≥75 years diagnosed with DED (Farrand et al, 2017).

DED is a multifactorial disorder of the tear film and ocular surface that results in eye discomfort, visual disturbances, tear film instability, and often ocular surface damage (Perry, 2008; Schultz, 2014). In humans, dry eye was found to be associated with the presence of conjunctival T-cells and elevated levels of inflammatory cytokines in the tears compared with controls (Massingale et al, 2009; Lee et al, 2013).

Investigational Product Rationale

In order to address the limitations of topical ophthalmic eye drops, Ocular Therapeutix has developed OTX-CSI (cyclosporine ophthalmic insert) for intracanalicular use. OTX-CSI combines the benefits of cyclosporine with punctal occlusion, an effective therapy for DED (McCabe, 2009). OTX-CSI contains approximately 0.36 mg of cyclosporine and is designed to deliver therapeutic levels of cyclosporine onto the ocular surface for a duration of approximately 12 weeks. Continuous release of cyclosporine from the hydrogel inserts may result in higher daily concentrations of cyclosporine delivered to the ocular surface than is found with topical Restasis.

Considering the low cyclosporine concentrations required at the ocular surface, OTX-CSI, offers promise as a potential sustained release treatment for patients with signs and symptoms of DED for approximately 12 weeks with a single insert.

The two active formulations of OTX-CSI being studied in this clinical trial contain the same cyclosporine dose and release drug at the same daily rates but differ in their hydrogel composition. These two formulations are designed to have different breakdown periods of the hydrogel with one formulation designed to last approximately 2 to 3 months (Formulation 1 (F1)) and the other approximately 3 to 4 months (Formulation 2A (F2A)).

Sponsor:	Ocular Therapeutix, Inc.			
Protocol:	CLN-Protocol-0054			
Document Version No.:	V1.0	Document Date:	01-OCT-2021	

The two HV insert formulations being studied contain no active drug but differ in their hydrogel formulation. These two formulations are designed to have different hydrogel breakdown periods with one formulation designed to last approximately 1 week (Formulation 3 (F3)) and the other approximately 3 to 4 months (Formulation 2B (F2B)).

Sponsor:	Ocular Therapeutix, Inc.			
Protocol:	CLN-Protocol-0054			
Document Version No.:	V1.0 Document Date: 01-OCT-2021			

2. STUDY DESIGN

2.1. Synopsis of Study Design

This is a randomized, multi-center, double-masked, vehicle-controlled, phase 1/2 clinical study designed to evaluate the safety, tolerability, and efficacy of OTX-CSI (cyclosporine ophthalmic insert) for intracanalicular use for the treatment of subjects with DED. Approximately 145 subjects (290 eyes) will be enrolled in this study at approximately 15 sites in the US.

Subjects will be enrolled in two cohorts. Cohort 1 will be an open-label group consisting of approximately 5 subjects. Cohort 2 will be a randomized, double-masked group consisting of approximately 140 subjects treated with 2 different hydrogel formulations of OTX-CSI and 2 different formulations of hydrogel vehicle inserts (HV). Both eyes will be treated with the same treatment/formulation.

Cohort Number	Number of Subjects	Treatment	Formulation
1 Open-label	5	OTX-CSI	2A
2 Randomized, double-masked	40	OTX-CSI	1
	40	OTX-CSI	2A
	40	HV	2B
	20	HV	3

Cohort 1

Subjects in Cohort 1 will undergo Screening 14 days prior to Insertion/Day 1 (Visit 2) to determine eligibility and eligibility will be re-confirmed at Visit 2 (Insertion/Day 1). The treatment follow-up visits will occur at Week 2 (Visit 3), Week 4 (Visit 4), Week 6 (Visit 5), Week 9 (Visit 6), Week 12 (Visit 7), and Week 16 (Visit 8). All subjects in Cohort 1 will be followed until Week 16 (Visit 8) whether or not an insert is visualized.

Cohort 2

Subjects in Cohort 2 will undergo Screening 14 days prior to Insertion/Day 1 (Visit 2) to determine eligibility. At Visit 2 (Insertion/Day 1) eligibility will be confirmed and subjects who are eligible will be randomly assigned to one of four treatment groups (OTX-CSI Formulation 1, OTX-CSI Formulation 2A, HV Formulation 2B or HV Formulation 3) in a 2:2:2:1 ratio. Should only a unilateral insertion be possible, Visit 2B will occur within 3 days to attempt the insertion again. The treatment follow-up visits will occur at Week 2 (Visit 3), Week 4 (Visit 4), Week 6 (Visit 5),

Sponsor:	Ocular Therapeutix, Inc.			
Protocol:	CLN-Protocol-0054			
Document Version No.:	V1.0	Document Date:	01-OCT-2021	

Week 9 (Visit 6), Week 12 (Visit 7), and Week 16 (Visit 8). All subjects in Cohort 2 will be followed until Week 16 (Visit 8) whether or not an insert is visualized.

[figure not shown]
For both cohorts, if an OTX-CSI or HV insert is visualized in either eye or both eyes at Week 16 (Visit 8) the subject will return to the clinic in 30 days (\pm 10 days; Visit 9) and will continue returning to the clinic every 30 days as needed until an insert can no longer be visualized and the physician has determined that there is no evidence of biological activity. Additionally, subjects may be exited any time at the investigator's discretion. If an OTX-CSI or HV insert cannot be visualized at Week 16 (Visit 8) and the physician has determined that there is no evidence of biological activity, the subject will exit the study.

This study will be conducted per the schedule shown in Figure 1.

[figure not shown]
Statistical Analysis Plan

Sponsor:	Ocular Therapeutix, Inc.			
Protocol:	CLN-Protocol-0054			
Document Version No.:	V1.0	Document Date:	01-OCT-2021	

Figure 1 Cohort 1 and Cohort 2 Study Schematic

^{*}Subject remains in study until insert is no longer visible and no evidence of biological activity.

CRS-BS-TP-000005 V 1.0

Page 15 of 50

Client / Cytel Confidential: This is a controlled document and shall not be changed, saved, copied or reproduced by any unauthorized person.

Sponsor:	Ocular Therapeutix, Inc.			
Protocol:	CLN-Protocol-0054			
Document Version No.:	V1.0 Document Date: 01-OCT-2021			

2.2. **Objectives of Statistical Analysis**

The objectives of the trial with respect to Cohort 1 are to assess the safety and tolerability of OTX-CSI in subjects with DED. The objectives of the trial with respect to Cohort 2 are to assess the safety, tolerability, and efficacy of OTX-CSI in subjects with DED.

2.3. Randomization Methodology and Masking

Cohort 1 will be open-label and treatment assignment will be known to the sponsor, investigator and subjects. All 5 enrolled subjects in Cohort 1 will receive OTX-CSI Formulation 2A.

Cohort 2 will be randomized to treatment assignment and double-masked.

A randomization schedule will be computer-generated by a qualified biostatistician independent of the study conduct or project team and uploaded into the EDC system. The EDC/IRT system will be used for randomization and unmasking. At Visit 2 (Insertion/Day 1) eligibility will be confirmed and subjects who are eligible will be randomly assigned to one of four treatment groups (OTX-CSI Formulation 1, OTX-CSI Formulation 2A, HV Formulation 2B or HV Formulation 3) in a 2:2:2:1 ratio.

The HV and OTX-CSI inserts administered to subjects at randomization in the double-masked treatment phase will be comparable in appearance. Study subjects and investigators and their staff will be masked to the identity of treatment until the final database is locked. The Sponsor's personnel involved with the conduct and monitoring of the study will remain masked until completion of the study and database lock.

2.4. Stopping Rules and Unmasking

Appropriate precautions must be taken to prevent unauthorized access to the randomization scheme. Unless the subject's safety requires otherwise and if time permits, the decision to unmask a treatment assignment is to be made jointly by the Investigator and Sponsor's medical monitor.

If unmasking is required, the integrity of the study assessments and objectives will be maintained by limiting access to the unmasked data to the two individuals in the Safety Review Group (Sponsor Medical Monitor and Sponsor Statistician) who are not involved in the study conduct or directly by the investigator if required in an emergency.

2.5. **Study Procedures**

The Time and Events Schedule, as outlined in the study protocol, is provided in Table 1.

Sponsor:	Ocular Therapeutix, Inc.			
Protocol:	CLN-Protocol-0054			
Document Version No.:	V1.0 Document Date: 01-OCT-2021			

Table 1 Time and Events Schedule

Study Parameter*	Screening/ Baseline Visit Day -14	Insertion Day Day 1	Follow-up Week 2 ±2 days	Follow-up Week 4 ±2 days	Follow-up Week 6 ±3 days	Follow-up Week 9 ±3 days	Follow-up Week 12 ±3 days	Final Visit Week 16 ⁸ ±3 days	30-Day Follow-Up Visit ⁹ (± 10 days)
Visit	1	2	3	4	5	6	7	8	9
Informed Consent	Х								
Determine Eligibility	Х	Х							
Demographic Information	Х								
Medical/Ophthalmic History	Х								
Record Medications	Х	Х	Х	Х	X	Х	Х	Х	Х
Record Adverse Events ¹⁰		Х	Х	Х	Х	Х	Х	Х	Х
Urine Pregnancy Test ¹	Х							Х	
OSDI	Х	Х	Х	Х	X	Х	Х	Х	Х
VAS for Eye Dryness	Х	Х	Х	Х	X	Х	Х	Х	Х
SPEED	Х	Х	Х	Х	X	Х	Х	Х	Х
Corneal Fluorescein Staining Using the NEI Scale	Х	Х	Х	Х	X	Х	Х	Х	Х
Conjunctival Lissamine Green Staining Using the NEI Scale	Х	Х	Х	Х	X	Х	Х	Х	Х
Assessment of BCVA	Х	Х	Х	Х	X	Х	Х	Х	Х
Slit Lamp Biomicroscopy (including punctum assessment)	Х	X^4	Х	Х	X	Х	Х	Х	Х
OTX-CSI or HV Insert Presence by Visual Assessment			Х	Х	X	Х	Х	Х	Х
Ease of Visualization as assessed by Investigator			Х	Х	X	Х	Х	Х	Х
Systemic PK sample collection ² (at selected sites)		X ⁵	Х						
Tear Film PK sample collection ⁷ (at all sites)		X^6	Х	Х	X	Х	Х	Х	Х
Measurement of TBUT	Х	Х			X		Х		
Schirmer Test (without anesthesia)	Х	Х	Х	Х	X	Х	Х	Х	Х
IOP Measurement	Х	Х						Х	
Fundus Exam ³	Х							Х	
Punctum Size Assessment		Х						Х	

Sponsor:	Ocular Therape	Ocular Therapeutix, Inc.			
Protocol:	CLN-Protocol-0054				
Document Version No.:	V1.0 Document Date: 01-OCT-2021				

Table 1 Time and Events Schedule – continued

Study Parameter*	Screening/ Baseline Visit Day -14	Insertion Day Day 1	Follow-up Week 2 ±2 days	Follow-up Week 4 ±2 days	Follow-up Week 6 ±3 days	Follow-up Week 9 ±3 days	Follow-up Week 12 ±3 days	Final Visit Week 16 ⁸ ±3 days	30-Day Follow-Up Visit ⁹ (± 10 days)
Visit	1	2	3	4	5	6	7	8	9
Randomization (Cohort 2)		Х							
OTX-CSI or HV Insert Placement		X ^{11 & 12}							
Ease of Insertion as assessed by the Investigator		Х							
Dispense Artificial Tears (as needed)	Х	Х	Х	Х	X	Х	Х		
Dispense Daily Subject Diary for Artificial Tear Use (as needed)	X	Х	Х	Х	X	х	Х		
Collect/review Daily Subject Diary for Artificial Tear Use (as needed)		Х	Х	Х	X	Х	Х	Х	

*All examinations need to be performed on both eyes. See Section 8.4 to confirm the order that the assessments should be performed.

1 A negative UPT is required for women of childbearing potential to be included in the study.

- 2 Select sites will collect Systemic PK. All sites will collect Tear Film PK.
- 3 Dilated fundus examination at screening; undilated fundus examination at Week 16.
- 4 Prior to insertion, a clinical determination of the absence of infection will be made based on the lack of erythema or discharge at the punctum.
- 5 Systemic PK sample on Day 1 will be collected after successful insertion at 2 hours (±30 minutes) or 4 hours (±30 minutes) post-insertion.
- 6 Tear Film PK will be collected at 1 hour (±30 minutes), 2 hours (±30 minutes), and 4 hours (±30 minutes) post insertion on Day1. Tear Film PK should be collected using Schirmer strips.
- 7 Tear Film PK will be collected using Schirmer Tests strips. These will be collected and sent to the central lab for analysis. See lab manual.
- 8 Early termination subjects should complete assessments based on the final visit (Visit 8) schedule of assessments.
- 9 Post week 16 visit will be conducted every 30 days (± 10 days) until an insert can no longer be visualized and the physician has determined that there is no evidence of biological activity. Additionally, subjects may be exited at the investigator's discretion
- 10 Signs, symptoms, conditions occurring prior to insertion on Day 1 should be captured as medical history.
- 11 For Cohort 1 subjects only, within the first six weeks post treatment, if an insert is not visualized in one or both eyes by the Investigator, the Investigator should place a new insert in the respective eye(s) after confirming patency. Refer to Appendix 13 for placement instructions. Replacement of inserts for Cohort 2 subjects is not permitted.
- 12 If placement is only successful in one eye, subjects should be asked to return within 1-3 days to attempt insertion in the other eye. The following items should be repeated at the return visit, Insert Placement, Ease of Insertion, Tear Film PK and AEs.

Sponsor:	Ocular Therape	Ocular Therapeutix, Inc.			
Protocol:	CLN-Protocol-0054				
Document Version No.:	V1.0 Document Date: 01-OCT-2021				

2.6. Efficacy and Safety Variables

2.6.1. Efficacy Variables

2.6.1.1. Primary Efficacy Variable

1- Schirmer Test (mm) and its change from baseline (CFB) at Week 12

2.6.1.2. Secondary Efficacy Variables

- 1- Percent of eyes with ≥10 mm Increase in Schirmer Test from Baseline at Week 12
- 2- Eye Dryness Severity and Frequency Scores (VAS) and their CFB to each post-baseline visit.
- 3- Schirmer Test (mm) and its change from baseline (CFB) to each post-baseline visit.
- 4- Total Corneal Fluorescein Staining (tCFS) using National Eye Institute (NEI) scale and its CFB to each post-baseline visit.
- 5- CFS sub-regions using NEI scale and its CFB to each post-baseline visit.
- 6- Conjunctival Lissamine Green Staining using NEI scale and its CFB to each post-baseline visit.
- 7- Ocular Surface Disease Index questionnaire (OSDI©) (total score, each of the three domains and the individual questions) and its CFB to each post-baseline visit.
 - OSDI total score will be calculated using below OSDI© formula:

$$Overall \ OSDI \ score \ = \frac{(Sum \ of \ scores \ for \ all \ questions \ answered) \ \times \ 25}{number \ of \ questions \ answered}$$

OSDI score for each section (ABC) will be calculated using below formula:

OSDI score for each section (A, B, C)

```
=\frac{(Sum of scores for all questions answered for the section) \times 25}{number of questions answered in that section}
```

The OSDI is scored on a scale of 0 to 100, with higher scores representing greater disability.

- 8- SPEED measures (overall score and individual questions) and its CFB to each postbaseline visit.
 - SPEED overall score will be calculated as Sum of the questions in frequency and severity of symptoms.

Sponsor:	Ocular Therapeutix, Inc.			
Protocol:	CLN-Protocol-0054			
Document Version No.:	V1.0 Document Date: 01-OCT-2021			

The final score ranges from 0 to 28, with higher scores representing the severe dryness.

2.6.2. Safety Variables

The safety variables are as follows:

- 1- Ocular and non-ocular adverse events
- 2- Best Corrected Visual Acuity (BCVA): LogMAR Visual Acuity (VA) score at each visit and its CFB at each post-baseline visit
- 3- Slit-Lamp biomicroscopy parameters by location (Eyelid Vascularity (vascular engorgement), Vascular, Engorgement of Eyelid Margin of upper and lower lid, Punctal Appearance, Lid Apposition, Lashes, Conjunctiva, Sclera, Cornea, Anterior Chamber, Iris, Pupil, Lens) by visit
- 4- Intraocular Pressure (IOP) measurement (mmHg) and its CFB by visit
- 5- Fundus Examination: Vitreous, Retina, Macula, Choroid, Optic nerve by visit
- 6- Artificial tears use during the study: the use of Artificial tears since last visit at each postbaseline visit.

Sponsor:	Ocular Therapeutix, Inc.			
Protocol:	CLN-Protocol-0054			
Document Version No.:	V1.0 Document Date: 01-OCT-2021			

3. SUBJECT POPULATIONS

3.1. **Population Definitions**

1. Intent-to-Treat (ITT): The ITT population will include all randomized subjects.

2. **Modified Intent-to-Treat (mITT)**: the Modified ITT population is defined as all subjects in ITT who received the insert, investigational product (IP) (OTX-CSI or HV). The mITT population will be used as the primary efficacy analysis population and will be performed for all efficacy endpoints.

3. **Per Protocol (PP):** includes all mITT subjects who do not have any major protocol deviation which is likely to seriously affect the safety and efficacy outcomes of the study and who do not report excessive artificial tear use defined as greater or equal to 60 drops between Week 9 (Visit 6) and Week 12 (Visit 7). Analysis on the PP population will be used as secondary efficacy analysis and will be performed for select efficacy endpoints, analyzing subjects under the treatment actually received. Important protocol deviations will be identified prior to locking the study database.

4. **Safety Set (SAF):** includes all subjects who received investigational product (IP) (OTX-CSI or HV) from Cohort 1 and Cohort 2. Analyses performed on the Safety population will be according to the treatment the subject actually received.

5. **Cohort 1 population:** Cohort 1 population will include all subjects who received IP. Demographic and baseline characteristics, other ocular examination data, and safety data will be summarized.

3.2. **Protocol Deviations**

At the discretion of the sponsor, major protocol deviations as determined by a review of the data prior to unmasking of the study results and the conduct of statistical analyses may result in the removal of a subject's data from the PP Population. This file will include a description of the protocol deviations, and classification of major or minor protocol deviations. It will be finalized prior to hard database lock and unmasking. Major protocol deviations will be summarized by treatment groups and overall. The data listing for all protocol violations will be also presented.

Sponsor:	Ocular Therape	Ocular Therapeutix, Inc.			
Protocol:	CLN-Protocol-0054				
Document Version No.:	V1.0	V1.0 Document Date: 01-OCT-2021			

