8.3.11 Replacement of Inserts

For Cohort 1 subjects only, within the first six weeks post treatment, if an insert is not visualized in one or both eyes by the Investigator, the Investigator should place a new insert in the respective eye(s) after confirming patency. Refer to Appendix 13 for placement instructions. Replacement of inserts is not permitted for subjects enrolled in Cohort 2.

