4.2.2. Unit of Analysis

Both eyes will be treated with the same treatment/formulation. If both eyes qualify, the eye having the higher total corneal fluorescein staining score will be designated as the study eye and the other eye designated as the non-study eye. If both eyes have the same total corneal fluorescein staining score, the study eye will be designated randomly, and the other eye designated as the non-study eye. If only one eye qualifies, that eye will be the study eye, but both eyes will still receive the same treatment/formulation.

The unit of analysis in this study will be the study eye (primary study eye) for all efficacy summaries. Efficacy summaries will be presented for both study and non-study eyes for Cohort 1 and Cohort 2. Cohort 1 will be included for all safety summaries and will include summaries of both study and non-study eyes. All primary, sensitivity, secondary, and exploratory endpoints will be analyzed for both study and non-study eyes, separately. All summaries will be presented by treatment groups and visits, where appropriate. In addition to summarizing the individual formulations, the two formulations of OTX CSI will be combined and summarized.

4.2.3. **Computing Environment**

All descriptive statistical analyses will be performed using SAS statistical software (Version 9.4), unless otherwise noted. Medical History and adverse events will be coding using Medical Dictionary for Regulatory Activities (MedDRA) version 24.0 - Mar 2021. Concomitant medications will be coded using World Health Organization (WHO) DD B3 WHO Drug DDE – Sep 2019.

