4.9. Safety Analyses

All safety analyses will be conducted on the Safety Population.

Adverse Events

Adverse events will be coded using the MedDRA Version 24.0 - Mar 2021 and displayed in tables and listings using System Organ Class (SOC) and Preferred Term (PT).

Analyses of adverse events will be performed for those events that are considered treatment emergent adverse events (TEAE), where treatment emergent is defined as any adverse event with onset on or after the first dose of study medication through the end of the study or any event that was present at baseline but worsened in intensity or was considered drug-related by the investigator through the end of the study.

The safety will be assessed by incidence of TEAEs, therefore, in any tabulation, a subject contributes only once to the count for a given adverse event (SOC or preferred term). An overall summary of TEAEs will be presented including the number of events and the number of the subjects with events along with percentages by treatment group and overall. The overall summary will include subjects with AE leading to death, subjects with TEAEs leading to insert removal and subjects with TEAEs leading to subject withdrawal. In summary tables, SOC will be presented alphabetically and events within SOC will be presented by decreasing frequency count based on the total column.

The frequency and percentage of subjects with any TEAEs and separately for ocular and nonocular TEAEs, with any ocular TEAEs by relationship to treatment (unrelated, related), with any ocular serious TEAEs by relationship to treatment (unrelated, related), with any TEAE by severity (mild, moderate, or severe), and with any serious adverse event (SAE) and separately for ocular and non-ocular events will be summarized by treatment group and overall.

All adverse events will be listed in subject data listings.

By-subject listings also will be provided for the following: subject deaths; serious adverse events; and adverse events leading to withdrawal.

Non-AE Safety Analyses

The following safety assessments will be summarized using descriptive statistics for Safety population by treatment group and overall. Assessments will be presented for study eye and non-study eye separately.

Sponsor:	Ocular Therapeutix, Inc.		
Protocol:	CLN-Protocol-0054		
Document Version No.:	V1.0 Document Date:		01-OCT-2021

1- Best Corrected Visual Acuity (BCVA)

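### Safety tables grouped by treatment received would mix about five open-label Cohort 1 subjects, whose inserts can be replaced, with the randomised F2A arm; Cohort 1 needs its own column

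*SAP*

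**What the plan says.** **Who is in the Safety Set.** SAP 3.1, item 4, says that it "includes all subjects who received investigational product (IP) (OTX-CSI or HV) from Cohort 1 and Cohort 2". The grouping rule follows: "Analyses performed on the Safety population will be according to the treatment the subject actually received". Cohort is not part of that rule.

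**What is run on it.** SAP 4.9 opens with "All safety analyses will be conducted on the Safety Population". Adverse events are summarised by treatment group and overall, and for the other assessments: "The following safety assessments will be summarized using descriptive statistics for Safety population by treatment group and overall". SAP 4.2.2 adds: "Cohort 1 will be included for all safety summaries and will include summaries of both study and non-study eyes". It also calls for a combined OTX-CSI summary.

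**What Cohort 1 receives.** SAP 2.3: "All 5 enrolled subjects in Cohort 1 will receive OTX-CSI Formulation 2A". Assignment is known to sponsor, investigator and subject; Cohort 2 is double-masked.

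**Insert replacement.** Protocol 8.3.11 begins "For Cohort 1 subjects only, within the first six weeks post treatment, if an insert is not visualized" and directs the investigator to place a new insert in the affected eye or eyes once patency is confirmed. The same section does not permit replacement in Cohort 2.

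**Signs of separate handling.** SAP 3.1, item 5, defines a Cohort 1 population and says of it: "Demographic and baseline characteristics, other ocular examination data, and safety data will be summarized". SAP 4.6 refers to the applicable cohort in one additional exposure analysis.

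**Planned tables.** In SAP 7.1, the deviation, baseline and medical history tables (14.1.3 to 14.1.6.3) name both mITT and Cohort 1. Table 14.1.8 (exposure) and the 14.3 tables are labelled for the Safety population, except 14.3.2.3 and 14.3.2.4, which carry no population label. None of them names Cohort 1.

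**The concern.** Adverse events are the primary safety evaluation (Protocol 6.2.1), and a reader will naturally look across the formulation columns. F1, F2B and F3 contain only randomised, masked subjects. If Cohort 1 is placed with F2A, that column alone also holds subjects who were neither randomised nor masked.

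Two features make this more than a matter of labelling:

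- **Knowledge of treatment.** Events are elicited by an open question (Protocol 10), and relatedness is a judgement (Protocol 10.7.2). Either can be influenced by knowing the assignment.
- **A different insertion rule.** Protocol 4.4 lists risks of the insertion procedure itself, and relatedness covers that procedure. Repeat insertions in Cohort 1 repeat that risk. SAP 4.6 counts exposure from the earliest insertion to the latest date an insert is confirmed absent, so a replacement can lengthen a subject's exposure in a way that cannot happen in Cohort 2.

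At stake is whether the F2A and combined OTX-CSI columns describe the randomised arm or a mixture.

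**Working it through.** **1. Reproduce the planned numbers.** Cohort 2 has about 140 subjects at 2:2:2:1 (SAP 2.1 and 2.3): 140 × 2/7 = 40 for each of F1, F2A and F2B, and 140 × 1/7 = 20 for F3. Adding 5 from Cohort 1 gives 145 subjects and 290 eyes, as SAP 2.1 states. SAP 4.1 has no power calculation to reproduce.

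**2. Follow a Cohort 1 subject through the rules.** The subject received the product, so enters the Safety Set (3.1). Treatment received is F2A (2.3). All safety output uses that set, by treatment group (4.9). No rule diverts the subject to another column, so the subject lands in F2A and in combined OTX-CSI.

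**3. Share of each column.**

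- F2A: 5/(40 + 5) = 11.1%
- Combined OTX-CSI: 5/(80 + 5) = 5.9%
- Overall: 5/145 = 3.4%

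Five is approximate. Withdrawn Cohort 1 subjects are replaced (SAP 4.2.8), and those already treated stay in the Safety Set. With six treated, the F2A share is 6/46 = 13.0%.

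**4. Effect on an F2A event rate.** Let e be the subjects with an event among 40 randomised, and c the number among 5 in Cohort 1. The shift is (e + c)/45 − e/40, which equals (1/9) × (c/5 − e/40): one ninth of the difference between the two cohorts' rates. The documents give no event rates, so those below are assumed. Cells show the pooled rate, with the shift in points.

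| Randomised F2A | c = 0 | c = 1 | c = 2 | c = 5 |
|---|---|---|---|---|
| 0/40 = 0% | 0.0% (0.0) | 2.2% (+2.2) | 4.4% (+4.4) | 11.1% (+11.1) |
| 4/40 = 10% | 8.9% (−1.1) | 11.1% (+1.1) | 13.3% (+3.3) | 20.0% (+10.0) |
| 8/40 = 20% | 17.8% (−2.2) | 20.0% (0.0) | 22.2% (+2.2) | 28.9% (+8.9) |
| 20/40 = 50% | 44.4% (−5.6) | 46.7% (−3.3) | 48.9% (−1.1) | 55.6% (+5.6) |

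With one or two Cohort 1 events, the shift runs from −3.3 to +4.4 points. The largest is +11.1, when all five have an event and none of the 40 does. For combined OTX-CSI the corresponding maximum is 5/85 = 5.9 points.

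**5. Effect on mean exposure.** Assume that a replacement F2A insert lasts its designed 3 to 4 months, taken as 90 to 120 days, and that the fellow eye holds no insert for that time. Each replaced subject then adds 90/45 = 2.0 to 120/45 = 2.7 days to a pooled F2A mean. The addition is smaller if the fellow eye keeps its insert, because SAP 4.6 counts until neither eye has one.

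**6. Compare the promise with the table list.** SAP 3.1, item 5, says Cohort 1 safety data will be summarised. SAP 7.1 names Cohort 1 in Tables 14.1.3 to 14.1.6.3 but in neither Table 14.1.8 nor any 14.3 title. The promised summary has no listed table.

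**The case against.** The best defence is that the SAP never says the two cohorts share a column. Item 4 of SAP 3.1 fixes membership and grouping, not layout. Item 5 sets up a separate Cohort 1 population with its own safety summary, and SAP 4.6 uses a cohort-specific rule. SAP 7.1 gives titles rather than shells, and a Safety label does not rule out a Cohort 1 column. Including Cohort 1 was also pre-specified: Protocol 11.2 puts it in all safety summaries, and Protocol 11.10 defines the Safety population as everyone who received product. Cohort 1 receives the same formulation on the same schedule to Week 16. In a Phase 1/2 study, describing all exposed subjects by treatment received is defensible, and by-subject listings are planned.

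Much of this stands. Pooling is the natural reading of the rules, not an explicit statement.

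A reader might go further and infer that a primary safety comparison of F2A with F2B loses its randomised basis. The documents do not support that. SAP 4.9 plans only descriptive summaries, and the named formulation contrasts in SAP 4.7 concern efficacy and exploratory endpoints. A reader might also infer that open-label reporting inflates the F2A rates. Nothing in the documents fixes the direction, and the table above shows shifts both ways.

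The defence does not close the gap. A Cohort 1 population with no listed safety table does not separate anyone, and the cohort-specific wording in SAP 4.6 covers one additional analysis only. A separate column is also fully compatible with including Cohort 1 in every safety summary.

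**Conclusion.** The point holds as a layout left unspecified, whose natural reading mixes cohorts, together with an inconsistency between SAP 3.1 and SAP 7.1. About 11% of the F2A column and 6% of the combined OTX-CSI column would be open-label subjects under a different insert-replacement rule. For event rates the likely effect is a few points either way, with a ceiling of 11.1 points for F2A. These sizes assume exactly five treated Cohort 1 subjects, full Cohort 2 arms and the illustrative event rates shown.

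No planned inference is at risk. Safety output is descriptive, and the efficacy populations (mITT and PP) derive from randomised subjects only. The change is worth making because the mixing falls on one active formulation and is easily avoided.

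**What to change.** In SAP 4.9, SAP 4.6 and the SAP 7.1 table list:

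- Show Cohort 1 F2A as its own column in the Section 14.3 tables and in Table 14.1.8.
- Limit the F2A and combined OTX-CSI columns to Cohort 2.
- Keep Cohort 1 in the overall total.
- Label the tables accordingly, and give Tables 14.3.2.3 and 14.3.2.4 the population label they lack.

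This also delivers the Cohort 1 safety summary promised in SAP 3.1. It costs one extra column and slightly smaller denominators: 40 rather than 45 for F2A, and 80 rather than 85 for combined OTX-CSI. It needs no new data and changes no clinical procedure.
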